While not expected to be related to study participation, over the course of the study the research staff may become aware of depressive symptoms among our participants. The study assessment includes the Edinburgh Postnatal Depression Scale (EPDS), a screen for depressive symptoms for use during the post-partum period, and a modification of the SCID-I Binge Eating Disorder module. Elevated depressive symptoms, suicidal ideation, and positive screen for binge eating disorder are exclusionary. Research staff will alert participants that their scores make them ineligible to participate, and will let them know that when depression is very high, it's best to focus on that first rather than focusing on multiple things such as depression plus weight loss. In the conversation for BED, we will let them know that the weight loss intervention is not an appropriate intervention because we don't provide psychological help in the intervention, and receiving professional help, specifically cognitive behavioral therapy, will be more beneficial to them. We will offer to send a list of local resources to these participants. If suicidal ideation is present, the program director will call to assess safety and suggest professional help if needed as described below. Women who score 12 or greater (suggestive of high risk of clinical depression) and score negative on the EPDS suicide question (#10) will be encouraged to contact their provider to discuss their symptoms. After consulting with the PI, research staff will also contact the participant's PCP/OBGYN and let her/him know that the participant's score was suggestive of depression. Women who score positive on the EPDS suicide question (#10) will be considered at acute risk of injury or harm. In the unlikely event, the study PI [name], clinical psychologist Co-I [name], or project director [name] will be contacted immediately and the participant will be assessed for the need for immediate referral for psychiatric evaluation. Urgent evaluation will be arranged for the participant as indicated, and the participants' provider will be made aware of the situation. Staff will confirm participants' contact information prior to each study follow-up assessment including contact information for their PCP/OBGYN. In the case that a participant's EPDS score necessitates communication with her PCP/OBGYN and the participant reports not currently being under the care of either a PCP or an OBGYN, research staff will ask the participant whether she is being seen by another health care provider, and if so, ask the participant for contact information with the purpose of communicating with the provider about her depressive symptoms. In the case that the participant is not currently being seen by any health care provider, research staff will offer to send the participant information about mental health resources in her local area and will follow-up with the participant via phone and/or email until she has connected with a new healthcare provider, then contact the new provider per our protocol. Research staff will stop contacting participants after they have attempted to contact the participant on a maximum of 10 times over a maximum of 4 weeks. Participants will be made aware of this protocol in the original consent for the study. All referrals will be documented and reported to the study PI.

Inconveniences participants may experience include time spent to participate in the research. This includes time to travel to/from study assessments, and, for women randomized to the in-person condition, time to travel to/from the group meetings. We have planned study procedures to minimize the time needed by only collecting data needed to achieve study aims.

Participants may receive a benefit of weight loss, however since this is a research study this cannot be promised. If a participant expresses upset over lack of weight loss during the intervention period, research staff will encourage her to engage fully in the intervention and seek help from the counselor and other women in their group to make lifestyle changes supportive of weight loss. If a participant expresses upset with her weight loss following the intervention period, we will remind her that weight loss was not guaranteed, and encourage her to keep up with the healthy changes she made during the intervention or seek assistance with further weight loss from her PCP or OBGYN or by joining a formal weight loss program.

Benefits: [Describe anticipated benefits to the individual participants. If test results will be provided, describe and explain procedures to help participants understand the results. If individual participants may not benefit directly, state so here. Describe anticipated benefits to society (i.e., added knowledge to the field of study) or a specific class of individuals (i.e., athletes or autistic children). Do not include compensation or earned course credits in this section.]

Participants may or may not benefit from participating in the trial. Benefits that could occur are losing weight through the exercise and lifestyle intervention. Results from this research will help refine the delivery of this intervention with the intent of increasing the efficacy of the intervention.

Risk/Benefit Analysis: [Describe the ratio of risks to benefits. Risks to research participants should be justified by the anticipated benefits to the participants or society. Provide your assessment of anticipated risks to participants and steps taken to minimize these risks, balanced against anticipated benefits to the individual or to society.]

This research does not involve more than minimal risk/slight increase over minimal risk. As described above, we will take steps to minimize these risks. Participants may derive direct benefit from participation. Additionally, results are intended to benefit future populations of post-partum women.

Economic Considerations: [Describe any costs to the participants or amount and method of compensation that will be given to them. Describe how you arrived at the amount and the plan for compensation; if it will be prorated, please provide the breakdown. Experimental or extra course credit should be considered an economic consideration and included in this section. Indicate when participants will receive compensation.]

Facebook, My Fitness Pal, and time-tracking apps we will recommend do not cost any money to use. We will encourage participants to check their data usage plan to ensure they are using the appropriate settings on their phone to minimize the use of their data so they don't incur any charges due to any increased use of apps during participation in the study.

Participants will receive a \$20 gift card after completing the baseline assessment (visit and survey) and a \$40 gift card after completing each follow-up study assessment (6 months and 12 months) to compensate them for their time, for a total of \$100. Participants will be reimbursed up to \$5 for parking or bus fare for each study visit (both conditions) and group intervention session (participants randomized to the in-person condition), as needed.

Data Safety Monitoring: [This is a prospective plan set up by the study investigators to assure that adverse events occurring during studies are identified, evaluated, and communicated to the IRB in a timely manner. Although the investigators initially propose a Data Safety Monitoring Plan (DSMP), the IRB must approve the plan and may require revision of the plan. A DSMP is required for all human studies at the University of Connecticut except for studies determined to be exempt from continuing IRB

review. For studies that present more than minimal risk to participants, the IRB will review and determine on a case-by-case basis whether a data safety monitoring board is most appropriate. Please refer to the IRB's policy regarding data safety monitoring *before* completing this section - <http://research.uconn.edu/policies-procedures>.

Issues that should be addressed in the DSMP include the following:

1. frequency of the monitoring
2. who will conduct the monitoring (Under UConn policy a student cannot be the sole person responsible for monitoring the data and safety of the protocol procedures)
3. what data will be monitored (include compliance with approved IRB protocol)
4. how the data will be evaluated for problems
5. what actions will be taken upon the occurrence of specific events or end points
6. who will communicate to the IRB and how communication will occur
7. describe procedures to inform the sponsor

Sample response to issues listed above for minimal risk/ slight increase over minimal risk – “Survey results will be monitored by the PI in conjunction with the student investigator once every two weeks (items 1, 2 and 3). Survey responses will be reviewed to monitor for clarity (i.e., the same question is skipped by 5 or more participants). In that case, the question will be revised and an amendment will be submitted to the IRB (items 4, 5 and 6).”

Every two weeks (item 1), the PI and research coordinator (item 2) will review survey responses and collection and storage of additional data (item 3) to insure compliance with study protocols (item 4). Any deviations to protocol or adverse event reported by participants will be reported to the IRB through the appropriate process via InfoEd (item 5) by the PI (item 6), and we will submit an amendment if appropriate (item 5). The report of adverse events is built into our tracking database. Staff will assess the presence of adverse events during all participant contacts. We will report to NIH any serious unanticipated harms or unexpected threat to privacy as appropriate (item 7). We will convene a Data Safety and Monitoring Board (DSMB) to monitor the safety of participants throughout the proposed research, in particular for the occurrence of adverse events (both serious and otherwise). See attached grant proposal section 6 (pages 30-31).

Privacy/Confidentiality Part 1: [Explain how the privacy interests of participants will be maintained during the study (note that **privacy pertains to the individual not to the data**). Describe how data will be coded. Do not use any potentially identifiable information such as initials of participants as part of the code. If identifiable, sensitive information (illegal drug use, criminal activity, etc.) will be collected, state whether a Certificate of Confidentiality will be obtained. Be sure to state whether any limits to confidentiality exist and identify any external agencies (study sponsor, FDA, etc.) that will have access to the data. If participants will be screened, describe the plans for storage or destruction of identifiable data for those that failed the screening.]

Each participant will be assigned a unique study ID number that does not include any potentially identifiable information such as initials as part of the code. We will ask participants not to share information they learned about other participants during the group with others outside of the group. Investigators and research staff undergo training to help participants feel at ease with the study and to understand how their information will be protected. The research team will not access information about a participant after data have been collected except on an as-needed basis (such as to correct a telephone number).

During the study, should the research team become aware of any changes made to the privacy policies of Facebook, My Fitness Pal, or any time-tracking app recommended, research staff will notify participants that the policy has been updated and will encourage participants to review their privacy settings. The private (secret) Facebook group will be deleted by research staff 6 months after the last post or reply posted by a research participant. Photographs uploaded to Facebook by participants during the study will be accessible to participants as with any photo they upload to Facebook; research staff will not download participant photographs from Facebook when capturing engagement data.

Data from ineligible participants: Contact information will be stored in a file with an indication that they are not eligible and reason(s) for ineligibility. After enrollment is complete, data collected from the screening, including reason ineligible, will be stored in a de-identified dataset.

The identified data will be kept in a locked cabinet and/or electronically using password-protected and encrypted files. Any study documents containing identifying information or other sensitive data will be transported in a lockbox. Data from paper forms (e.g., eligibility screeners, contact information sheet, Facebook post rating forms) will be entered by research staff into REDCap. Study documents will be retained for at least 3 years after the completion of the research as required by Federal regulations. Downloaded datasets will be kept on password-protected research drive accessible only by appropriate research staff. Study documentation will be kept on password-protected research drives and/or locked filing cabinets in the PI's office. The link between identifiable information will be maintained in a REDCap database. Access to the REDCap database will be limited only to appropriate research staff. The link between identifiable information and de-identified study data will be deleted after all study procedures are completed and permanent de-identified study datasets have been created. The PI is responsible for the management of data.

Research staff will transcribe focus group discussions. During transcription of focus group audio recordings, participants' names will be replaced with an identification number to permit linking of statements with de-identified survey data. Uniquely identifying statements (e.g., names of people or companies) will be masked during transcription. After the recordings have been checked for accuracy they will be deleted. Interview transcripts will be stored on a password-protected research drive accessible only by appropriate research staff. When the research results are published or discussed in conferences, manuscripts or grants, no information will be included that reveals patient identity.

The following security protocols will also be applied to all data: physical protections -- all recordings and data will be stored on secure servers behind firewalls. All hard copy files will be locked in secure cabinets; logical protections – all recordings and data will be password protected and/or encrypted; and access protections – access will be granted to data on a need to know basis only. All records consisting of personal identifiers will be destroyed upon completion of the study by shredding of the hard paper copy, redacting the PHI/PII from the hard paper copy, and/or destruction of the electronic files.

Privacy/Confidentiality Part 2: Complete the Data Security Assessment

Form: [This form IS REQUIRED for ALL studies. The form is available here - <http://research.uconn.edu/irb/irb-forms-infoed/>. This form will be used to assess procedures for protecting confidentiality of data collected during the study and stored after closure. It will also be used to assess plans for storage and security of electronic data in accordance with University Best

Practices. Review the document proving tips to complete the form located at <http://content.research.uconn.edu/pdf/storrs/rcc/irb/TipsDataSecurityAssessmentForm.docx>.

The Data Security Assessment Form is enclosed.

Informed Consent

As PI, you are responsible for taking reasonable steps to assure that the participants in this study are fully informed about and understand the study. Even if you are not targeting participants from “Special Populations” as listed on page 4, such populations may be included in recruitment efforts. Please keep this in mind as you design the Consent Process and provide the information requested in this section.

Consent Setting: [Describe the consent process including *who* will obtain consent, *where* and *when* will it be obtained, and *how* much time participants will have to make a decision. Describe how the privacy of the participants will be maintained throughout the consent process. State whether an assessment of consent materials will be conducted to assure that participants understand the information (may be warranted in studies with complicated study procedures, those that require extensive time commitments or those that expose participants to greater than minimal risk).]

During eligibility screening, study staff will describe the study and answer any questions about participation. This process is intended to ensure that they understand the procedures, risks, and benefits involved in study participation. The consent process will take place at the baseline assessment. Ample time will be allowed for discussion or questions. Participants will be given enough time as needed to review the consent form and ask any questions prior to signing. Prior to signing the consent form, we will provide a verbal review of the consent form and allow time for questions to make that the participant understands all sections on the form and all aspects of study participation. This verbal review and questions will occur during screening, and we will provide the participant a copy of the consent form in advance of the baseline assessment either in hard-copy or via email. Before signing, research staff will verbally review the consent again and answer any questions before asking participants to sign. On the last page of the consent form the participant and the research staff member obtaining the consent will sign and date the form. We will ask participants to sign two copies of the consent form; following staff signature, we will provide participants with one of these copies.

Capacity to Consent: [Describe how the capacity to consent will be assessed for participants with limited decision-making capacity, language barriers or hearing difficulty. If a participant is incapable of providing consent, you will need to obtain consent from the participant’s legal guardian (please see the IRB website for additional information).]

All participants must be capable of providing informed consent. Eligible individuals must be able to complete the eligibility screening process in English and must endorse that they feel comfortable reading and writing in English in order to participate. The screening and consent process will include discussion of what participating in the study involves, including risks and benefits. If research staff conducting eligibility screening or obtaining informed consent has concerns about an individual’s ability to understand the study or her decision-making capacity, the case will be discussed with the PI who will determine whether to exclude the individual from participation on this basis.

Parent/Guardian Permission and Assent: [If enrolling children, state how many parents/guardians will provide permission, whether the child’s assent will be obtained and if assent will be written or oral. Provide a copy of the script to be used if oral assent will be obtained.]

N/A.

Documentation of Consent: [Specify the forms that will be used for each participant population, i.e., adult consent form, surrogate consent form, child assent form (written form or oral script) or an information sheet. Copies of all forms should be attached to this application in the same format that they will be given to participants (templates and instructions are available on the IRB website).]

Written informed consent will be obtained. The consent form is enclosed.

Waiver or Alteration of Consent: [The IRB may waive or alter the elements of consent in some minimal risks studies. If you plan to request either a **waiver of consent** (i.e., participants will not be asked to give consent), an **alteration of consent** (e.g., deception) or a **waiver of signed consent** (i.e., participants will give consent after reading an information sheet), please answer the following questions using specific information from the study:]

Waiver (i.e. participants will not be asked to give consent) or alteration of consent (e.g. use of deception in research):

- Why is the study considered to be minimal risk?
- How will the waiver affect the participants' rights and welfare? The IRB must find that participants' rights are not adversely affected. For example, participants may choose not to answer any questions they do not want to answer and they may stop their participation in the research at any time.
- Why would the research be impracticable without the waiver? For studies that involve deception, explain how the research could not be done if participants know the full purpose of the study.
- How will important information be returned to the participants, if appropriate? For studies that involve deception, indicate that participants will be debriefed and that the researchers will be available in case participants have questions.

Waiver of *signed* consent (i.e. participants give consent only after reading an information sheet):

- Why is the study considered to be minimal risk?
- Does a breach of confidentiality constitute the principal risk to participants? Relate this to the risks associated with a breach of confidentiality and indicate how risks will be minimized because of the waiver of signed consent.
- Would the signed consent form be the only record linking the participant to the research? Relate this to the procedures to protect privacy/confidentiality.
- Does the research include any activities that would require signed consent in a non-research setting? For example, in non-research settings, normally there is no requirement for written consent for completion of questionnaires.

We request a waiver of written consent to conduct eligibility screening. We will obtain verbal consent to conduct eligibility screening. Following eligibility screening, eligible individuals who indicate that they wish to participate in the research study will be asked for their full names, phone number, and email address. Staff will inform participants that we call and/or email them the day before their baseline assessment to remind them of appointment and confirm that they intend to attend, and that we plan on leaving a message if we do not reach them by phone. Participants may choose not to provide a phone number or email address if they do not wish to, or may request that we not leave a message on the phone's voicemail or answering machine.

Why is the study considered to be minimal risk? The probability and magnitude of harm or discomfort anticipated from the screening process is not greater than those ordinarily encountered in daily life or during the performance of routine psychological examinations or tests.

How will the waiver affect the participants' rights and welfare? Individuals may choose to not answer any eligibility screening questions they do not want to answer and may stop their participation in the eligibility screening at any time. However, all questions on the eligibility screener are required to determine eligibility for participation, so individuals who choose not to answer all questions will be excluded from further participation.

Why would the research be impracticable without the waiver? Given the study procedures, it would not be practical to obtain written informed consent before screening interested individuals for eligibility.

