The main purpose of the pilot trial is to examine the feasibility of recruitment (especially the proportion of women unwilling to be randomized to either condition), sustained participation, contamination, retention, and feasibility of assessment procedures, particularly measurement of cost-related data, in both treatment conditions, thus identifying modifications required before examining non-inferiority in a large randomized controlled trial. Leon, Davis, & Kraemer (2011) state "power analyses should not be presented in an application for a pilot study that does not propose inferential results."³¹ As they and others recommend,^{31,32} we based the sample size on necessities for examining feasibility, thus identifying modifications required to the design of the trial or study procedures before conducting the subsequent full-scale non-inferiority trial. Conducting two waves allows us to iteratively refine how we deliver intervention content via Facebook, and each wave includes n=36 women allows us to assess the feasibility of recruitment and engagement under the conditions of the subsequent trial. While we will aim to maximize retention in both conditions, with retention of $\geq 80\%$ to be acceptable, a priori, we decided that a retention rate in either condition lower than 60% would indicate that the non-inferiority trial is not feasible as designed. With n=36 per treatment condition, the 95% confidence interval (CI) for the estimated retention rate will be within $\pm 13\%$ if observed retention is 80%. Given n=36 per condition, the lower limit of the 95% CI for the observed retention rate in either treatment condition should not be lower than 60%.

We will enroll up to 125 participants with the intention of randomizing 72 participants. As the current study is a feasibility study, we are unsure the proportion of enrolled (consented) participants who will be randomized, as some participants will fail to complete baseline measures or may be found to be ineligible after baseline assessments.

For EACH Participant Population State Describe the Study Population(s): [Describe the participant population(s) including gender, ethnicity, income, level of education and age range.]

All participants will be adult women (aged 18 years or older). We anticipate minority enrollment of at least 30% as expected by the NIH/NHLBI. We are not targeting enrollment by income or level of education; we aim to recruit a diverse sample with respect to these characteristics.

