Baseline assessment. Staff will call and/or email participants within 3 days of their scheduled baseline assessment to remind them of the appointment. The baseline assessment will include informed consent measurement of height and weight, completion of a contact information sheet, and completion of additional measures which will be used to determine eligibility (screeners for depression and binge eating disorder). Study personnel will also help participants download My Fitness Pal app (all) and an app to track time on Facebook (Android users) and provide instruction of how to use these apps. For iPhone users, personnel will also show them how to locate Facebook app usage data using the battery settings. We expect the baseline study visit to take 30-45 minutes. Following the baseline assessment, research staff will fax the medical clearance form to participants' primary care provider or OBGYN. After the baseline visit, staff will email participants a link to complete a survey via REDCap. A copy of the baseline survey is enclosed. We will email participants a \$20 gift card after they have completed the baseline visit and online survey.

Orientation Webinar. Participants will complete a 60-minute orientation webinar. The purpose of the webinar is to educate participants about what research is, review study procedures, review importance of participation of enrolled participants, and to allow participants another opportunity to evaluate if joining this study is the right choice for them. This webinar is being conducted to improve study retention. The webinar moderator will record in REDCap tracking which participants completed the webinar.

Pre-Randomization Survey. Following the orientation webinar, we will email participants a short online survey that includes Facebook time measures and completion of a randomization agreement. We will email participants a copy of the randomization agreement form for their records. A copy of the pre-randomization survey is enclosed.

Participants will need to complete the telephone screening, baseline assessments (visit and survey), and orientation webinar, and pre-randomization survey before being randomized.

Randomization. We will randomize participants 1:1 to the FB and IP conditions in randomly permuted blocks of size 4 and 6. Randomization will be stratified by weeks post-partum at enrollment (8 weeks to <6 months, 6-12 months) and smartphone type (iPhone vs Android) .

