Weight loss intervention. The 6-month intervention will include dietary and exercise counseling and tips to help participants meet their healthy lifestyle goals. Participants will receive personalized calorie and physical activity goals to help them achieve a healthy weight loss of 1-2 pounds per week. Breastfeeding women will receive daily calorie goals that will facilitate weight loss while accounting for energy needs to support lactation; weight loss expectations do not differ by breastfeeding status. Participants will be encouraged to increase physical activity to 150 minutes per week of moderate intensity activity. While we will provide information about specific exercises designed to help with recovery from childbirth (e.g., pelvic floor exercises), participants will not be required to engage in any particular exercises or activity program. Counselors will encourage and support participants to make a plan for incorporating regular physical activity into their lives in a way (i.e., duration per session, frequency per week) that works for that individual woman. We will encourage participants to track their diet and exercise daily. We will encourage participants to use My Fitness Pal to track their diet and activity. In the in-person condition, the intervention will be delivered via weekly 90-minute group meetings for the first four months and then every other week in months 5 and 6. In the Facebook condition, the intervention will be delivered via a secret (private) Facebook group. See section 3.D.2.2.9 (3.D.2.2.9.1 through 3.2.2.9.6; pages 9-10) of the enclosed grant application for more details on the interventions.

Due to weather or to prevent spread of illness (e.g., coronavirus), we may hold intervention meetings for the in-person condition via video or telephone conference call.

Weekly time survey. Weekly, participants in both treatment conditions will complete a brief online survey to report current weight and time spent on Facebook. We expect the survey to take less than 5 minutes. The survey will be administered via REDCap. A copy of the weekly survey is enclosed.

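### The protocol says the lower 95% limit for retention should not fall below 60%, but with 36 women per condition that needs at least 27 or 28 retained, and the ±13% beside it is too favourable on the lower side

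*Protocol*

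**What the plan says.** The Protocol's Justification of Sample Size bases the sample size on feasibility and offers no power analysis. It calls retention of at least 80% acceptable. It also sets an a priori floor: "a retention rate in either condition lower than 60% would indicate that the non-inferiority trial is not feasible as designed".

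Two precision statements follow:

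- "With n=36 per treatment condition", "the 95% confidence interval (CI) for the estimated retention rate will be within" ±13% "if observed retention is 80" per cent.
- For the same 36 per condition, "the lower limit of the 95% CI for the observed retention rate in either treatment condition should not be lower than 60" per cent.

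The first is conditional on 80% observed retention. The second names no observed retention. Neither names an interval method, and neither says that women are treated as independent.

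On delivery, the same section says that "each wave includes n=36 women", in two waves. The Randomization paragraph says "We will randomize participants 1:1 to the FB and IP conditions". The Weight loss intervention paragraph describes group meetings for the in-person arm; for the other arm, "the intervention will be delivered via a secret (private) Facebook group".

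The Data Analysis section (Aim 1, Retention) defines retention as completion of the 6- and 12-month study visits, by condition. The SAP reports retention descriptively in each condition and specifies no interval.

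**The concern.** These two sentences are the only quantitative statement of what 36 women per condition can show. They stand directly after the floor that would mark the main trial as not feasible as designed. The side of the interval that matters is therefore the lower one. A symmetric interval near 80% with n=36 makes that side look shorter than a score or exact interval does.

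The second sentence matters more. Read as written, it tells the reader that a sample of this size keeps the lower limit at or above 60% in either condition. Whether it does depends on the retention observed. Between the 60% floor and about 75% to 78% observed retention, a condition would pass the floor while its interval still included values below 60%. A team relying on the sentence could report the pilot as having excluded retention below 60% when it had not.

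**Working it through.** **Inputs.** From the Justification of Sample Size: n = 36 per condition, 95% confidence (taken as two-sided, z = 1.96), observed retention 80%, floor 60%. The interval method is not given. Note that 80% of 36 is 28.8 women; the nearest attainable counts are 28 (77.8%) and 29 (80.6%).

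**1. Reproduce ±13%.** Wald half-width = 1.96 × √(0.8 × 0.2 / 36) = 1.96 × 0.0667 = 0.1307, giving 66.9% to 93.1%. The stated figure is correct for this method and independent women.

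**2. Score and exact intervals at 80%.** For Wilson, with z² = 3.84:

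- Centre = (0.8 + 3.84/72) / (1 + 3.84/36) = 0.8534 / 1.1067 = 0.771.
- Half-width = 1.96 × √(0.16/36 + 3.84/(4 × 36²)) / 1.1067 = 0.1275.
- Interval 64.4% to 89.9%.

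| Method, 80% of 36 | Interval | Below | Above | Total width |
|---|---|---|---|---|
| Wald | 66.9–93.1% | 13.1 | 13.1 | 26.1 |
| Wilson | 64.4–89.9% | 15.6 | 9.9 | 25.5 |
| Exact (Clopper-Pearson, evaluated at 28.8) | 63.3–91.4% | 16.7 | 11.4 | 28.1 |

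At the attainable 29/36, the lower sides are 15.6 points (Wilson) and 16.6 (exact).

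The Wald limit errs on the favourable side. If true retention is 80%, the Wald lower limit exceeds 80% once 33 or more women are retained. That has probability 5.2%, against a nominal 2.5%. For Wilson the count is 34 or more, with probability 1.6%.

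**3. When is the lower limit at least 60%?**

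| Retained | Observed | Wald lower | Wilson lower | Exact lower |
|---|---|---|---|---|
| 26/36 | 72.2% | 57.6% | 56.0% | 54.8% |
| 27/36 | 75.0% | 60.9% | 58.9% | 57.8% |
| 28/36 | 77.8% | 64.2% | 61.9% | 60.8% |
| 29/36 | 80.6% | 67.6% | 65.0% | 64.0% |

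The sentence therefore needs at least 27/36 by Wald and at least 28/36 by Wilson or exact. At 26/36 it fails by all three methods.

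**4. How often would it hold?** Assume true retention of 80% and independent women, so the count X is binomial (36, 0.8).

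- One condition: P(X ≥ 27) = 83% (Wald); P(X ≥ 28) = 72% (Wilson or exact).
- Both conditions, if the arms are independent: 0.832² = 69% (Wald); 0.716² = 51% (Wilson or exact).

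**5. Sensitivity to group delivery (assumed inputs).** Two waves of 36 with 1:1 allocation give 36/2 = 18 women per condition per wave. Treating these as two groups of 18 per condition is an inference, and the intraclass correlation (ICC) is an assumption. Design effect = 1 + 17 × ICC; effective n = 36 / design effect. At 80% observed retention:

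| Assumed ICC | Design effect | Effective n | Wilson lower |
|---|---|---|---|
| 0.01 | 1.17 | 30.8 | 62.9% |
| 0.02 | 1.34 | 26.9 | 61.6% |
| 0.05 | 1.85 | 19.5 | 58.1% |
| 0.10 | 2.70 | 13.3 | 53.2% |

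**The case against.** **There is no arithmetic error.** This stands. The ±13% follows from its own inputs, and Wald against Wilson or exact is a choice of method. Wilson is not wider overall; it is shifted down. At 80% with independent women, every method keeps the lower limit above 60% (66.9%, 64.4%, 63.3%). So the change of method alone does not overturn the protocol's conclusion at 80%.

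**The lower-limit sentence may be meant more narrowly.** It could continue the 80% example from the sentence before, or state a target. On the first reading it is true for independent women. But it repeats only the condition n = 36 and covers either treatment condition, so a reader can fairly take it as a property of the design. This objection supports rewording rather than leaving it.

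**Group delivery.** A reader might infer that clustering makes the lower limit fall below 60% even at 80% retention. The documents do not support that as a finding. They give no ICC for retention and do not state the number of in-person groups per wave; smaller groups would reduce the design effect. Retention is completion of study visits, not session attendance. The 12-month visits are individual, women who miss the 6-month focus group are offered individual assessments, and missed visits can be rescheduled up to five times. All this weakens the case for strong within-group correlation. At assumed ICCs of 0.01 and 0.02 the Wilson limit stays above 60%, and two groups per condition could hardly estimate an ICC. What remains is that independence is assumed without being stated.

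**The decision rule.** A reader might also infer that the feasibility rule tests the confidence limit. It does not: the floor is set on the retention rate itself, and the ±13% does not determine it.

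**Conclusion.** The point holds as a correction to two sentences. First, ±13% is a valid Wald figure but understates the distance to the lower limit: 15.6 points (Wilson) or 16.7 (exact) at 80%, against 13.1. Second, the unconditional lower-limit statement is not a property of n = 36. It requires at least 75% observed retention by Wald or 77.8% by Wilson or exact. Even with true retention at the acceptable 80%, it would fail in a given condition about 17% (Wald) or 28% (Wilson or exact) of the time.

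These results assume independent women and two-sided 95% intervals, and need no assumed ICC. The group-delivery figures are a sensitivity range only. Nothing here shows that the sample size is wrong or that the 60% floor should move. In a descriptive pilot this is a modest point, but it concerns the only precision claim the plan makes.

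**What to change.** In the Justification of Sample Size, and in the SAP's Retention paragraph where it concerns reporting:

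1. Replace ±13% with a named Wilson or exact interval and both limits at 80%: 64.4% to 89.9% (Wilson) or about 63.3% to 91.4% (exact).
2. Replace the lower-limit sentence with the condition it needs: at least 28 of 36 women (77.8%) retained in a condition.
3. Specify the same interval for reporting retention by condition.
4. State that the figures treat women as independent. Because both arms are delivered in groups, add one sensitivity sentence giving the Wilson lower limit at 80% for ICCs of 0.01 to 0.10 (62.9% to 53.2%), with the ICC and the two groups of about 18 per condition marked as assumptions.

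The cost is wording only: no more participants, no new data, and no change to the floor. The stated precision becomes slightly less favourable on the lower side.
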